## **CHAPTER FIVE**

### **CONCLUSION**

In conclusion, the use of adjunctive HP in custom fabricated trays presents with no adverse effects. Significant improvement was evident in pocket depth and attachment level in both treatment groups between after 4 weeks of using the tray. No significant effect found in SRP group between baseline and 4 weeks. After SRP, significant difference was seen in all three groups between 4 weeks and 3 months.

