## CHAPTER THREE

### RESULTS

There were total 15 subjects who completed the 6-month trial. There were 10 males with an mean age of 55.6 years and 8 males with an mean age of 51.1 years. There was a total of 3 patients in SRP group, 3 patients in HP13 group, and 9 patients in HP26 group. The mean pocket depth (PD) shown in figure 1 at baseline for SRP group was  $3.88 \pm 0.06$  mm (std. error),  $4.11 \pm 0.06$  mm for HP13, and  $3.83 \pm 0.04$  mm for HP26. At the 4-week examination, PD for SRP group decreased to  $3.67 \pm 0.06$  mm,  $4.06 \pm 0.06$  mm with HP13, and  $3.55 \pm 0.04$  mm for HP26. At the re-evaluation examination, PD for SRP group was  $3.30 \pm 0.06$  mm,  $3.43 \pm 0.06$  mm for HP13, and  $3.14 \pm 0.04$  mm for HP26. The final examination, PD were  $3.43 \pm 0.06$  for SRP,  $3.40 \pm 0.06$  mm for HP 13, and  $3.23 \pm 0.04$  mm for HP26. Repeated measure ANOVA showed significant difference in pocket depth among all time points in all treatment groups. In SRP group, no significant difference between baseline and 4 weeks in pocket depth and relative attachment level.

[figure not shown]

Figure 2. Mean PD in each group, SRP, HP13, and HP26.

Figure 2 shows the mean relative recession over time. The mean relative recession at baseline was  $3.28 \pm 0.06$  mm for SRP,  $2.87 \pm 0.06$  mm for HP13, and  $3.21 \pm 0.03$  mm for HP13. At 4-weeks, it was  $3.35 \pm 0.06$  mm for SRP,  $3.23 \pm 0.05$  mm for HP13, and  $3.15 \pm 0.03$  mm for HP26. At re-evaluation it was  $3.33 \pm 0.06$  mm for SRP,  $3.27 \pm 0.05$  mm for HP13, and  $3.29 \pm 0.03$  mm for HP26.

[figure not shown]

Figure 3. Mean R-Rec in each group, SRP, HP13, and HP26.

Figure 3 shows the mean relative attachment level. The mean RAL at baseline was  $7.16 \pm 0.08$  mm for SRP,  $6.97 \pm 0.07$  mm for HP13, and  $7.04 \pm 0.04$  mm for HP26. At 4-weeks, the RAL was  $7.02 \pm 0.08$  mm for SRP,  $7.29 \pm 0.07$  mm for HP13, and  $6.69 \pm 0.05$  mm for HP26. At re-evaluation the RAL was  $6.63 \pm 0.08$  mm for SRP,  $6.15 \pm 0.07$  mm for HP13, and  $6.39 \pm 0.04$  mm for HP26. At the final exam RAL was  $6.79 \pm 0.08$  mm for SRP,  $6.71 \pm 0.07$  mm for HP13, and  $6.53 \pm 0.04$  mm for HP26.

[figure not shown]

Figure 4. Mean RAL in each group, SRP, HP13, and HP26.

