## CHAPTER FOUR

### DISCUSSION

This randomized, examiner-blind, parallel-design, clinical trial compared the effectiveness of SRP to daily treatment with 1.7% hydrogen peroxide using prescription, custom-fabricated dental trays as an adjunct to SRP. The results of this study demonstrate that the peroxide/prescription tray treatment regimen in combination with SRP is statistically significant in terms of reduction of BoP

In contrast to prior studies (Putt 2012, 2013 Journal of Clinical Dentistry), this study did not provide evidence to show that the use of peroxide/prescription tray regimen prior to SRP would reduce pocket depths without mechanical intervention. According to Putt 2012, the mean difference between test and control group after two weeks of 4-times daily use hydrogen peroxide was 0.44 mm in sites >5mm. The difference between test and control groups for all sites was 0.18mm. The difference that was seen between our study was that the subjects were instructed to use twice daily hydrogen peroxide, therefore the total “contact time” of peroxide is effective half.

The amount of marginal tissue recession over time did not demonstrate an increase of soft tissue recession over time with the use of the prescription trays indicated that the physical seal along the gingival margin does not induce or propagate recession.

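### The claimed week-4 improvement in both tray arms is wrong for HP13 attachment and not credible for HP13 pocket depth, and no between-arm result supports the contrast with SRP

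*Combined protocol and SAP*

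**What the plan says.** The Conclusion, and the same sentence in the last paragraph of the Abstract, says: "Significant improvement was evident in pocket depth and attachment level in both treatment groups between after 4 weeks of using the tray". It goes on: "No significant effect found in SRP group between baseline and 4 weeks".

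The Results give the arm sizes: "There was a total of 3 patients in SRP group, 3 patients in HP13 group, and 9 patients in HP26 group". They print arm means for PD, relative recession (R-Rec) and RAL at each visit, each with a ± figure that the PD sentence identifies as a standard error. On testing they say "Repeated measure ANOVA showed significant difference in pocket depth among all time points in all treatment groups", and then "In SRP group, no significant difference between baseline and 4 weeks in pocket depth and relative attachment level". The text gives no p-value, confidence interval or SD of change, and no between-arm result for PD or RAL.

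The section on clinical periodontal parameters defines RAL as the distance from the stent margin to the pocket base, so a larger value is worse. The Statistical Analysis section lists PD reduction, RAL gain and BOP reduction as primary, averages PD per mouth, and plans ANCOVA using baseline for follow-up comparisons, two-sided at 0.05. The Discussion says that "this study did not provide evidence to show that the use of peroxide/prescription tray regimen prior to SRP would reduce pocket depths" in the absence of mechanical treatment.

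**The concern.** Week 4 closes the phase before any SRP, when the tray arms have had gel and the control arm has had neither gel nor debridement. It is the only point at which the gel is seen by itself, and the second primary objective concerns this phase. A reader of the Abstract or Conclusion learns that gel alone improved pocket depth and attachment in both tray arms while the control arm did not change. If the printed means do not bear that out for one of the two tray arms, a headline finding is wrong. The contrast is also built from separate within-arm verdicts, which do not estimate or test the difference between arms.

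**Working it through.** **Inputs.** Results chapter, mm, printed standard errors in brackets.

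| | SRP (n = 3) | HP13 (n = 3) | HP26 (n = 9) |
|---|---|---|---|
| PD, week 0 | 3.88 (0.06) | 4.11 (0.06) | 3.83 (0.04) |
| PD, week 4 | 3.67 (0.06) | 4.06 (0.06) | 3.55 (0.04) |
| R-Rec, week 0 | 3.28 | 2.87 | 3.21 |
| R-Rec, week 4 | 3.35 | 3.23 | 3.15 |
| RAL, week 0 | 7.16 (0.08) | 6.97 (0.07) | 7.04 (0.04) |
| RAL, week 4 | 7.02 (0.08) | 7.29 (0.07) | 6.69 (0.05) |

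The 3.21 is labelled HP13 in the text but fits HP26, since 3.83 + 3.21 = 7.04. There is no reported test statistic to reproduce, so the check starts from the means.

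**1. Do the HP13 figures hang together?** By definition RAL = PD + R-Rec. Week 0: 4.11 + 2.87 = 6.98 (printed 6.97). Week 4: 4.06 + 3.23 = 7.29 (printed 7.29). Both agree within rounding, so an isolated RAL misprint is unlikely.

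**2. Change, week 4 minus week 0.**
- PD: SRP −0.21, HP13 −0.05, HP26 −0.28.
- RAL: SRP −0.14, HP13 +0.32 (at least +0.31 after rounding), HP26 −0.35.

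HP13 attachment worsened. No choice of unit, test or correlation turns that into an improvement.

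**3. HP13 PD against SRP PD.** With separate paired t-tests (2 df, critical value 4.303), the largest SD of change that still gives p < 0.05 is |d| × √n / t:
- HP13: 0.05 × 1.732 / 4.303 = 0.020 mm. The SD must lie below this to be significant.
- SRP: 0.21 × 1.732 / 4.303 = 0.085 mm. The SD must lie above this to be non-significant.

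From the printed SEs, the SE of change is SE × √(2(1 − r)), where r is the correlation between visits. It is not given. On the t reference, HP13 is significant only if r > 0.98 and SRP non-significant only if r < 0.67. On the normal reference the limits are r > 0.91 and r < −0.59. A common method with similar r in the two arms cannot give both verdicts.

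**4. The other verdicts.** HP26 needs an SD of change below 0.28 × 3 / 2.306 = 0.36 mm (PD) and 0.35 × 3 / 2.306 = 0.46 mm (RAL), which is not demanding. SRP's non-significant PD change fits a patient-level test: with r = 0, 0.21 / 0.085 = 2.47 on 2 df, p = 0.13. For SRP RAL, 0.14 / 0.113 = 1.24, p = 0.34.

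**5. Differences from SRP in week 0–4 change.**
- HP13: PD −0.05 + 0.21 = +0.16; RAL 0.32 + 0.14 = +0.46 (worse).
- HP26: PD −0.28 + 0.21 = −0.07; RAL −0.35 + 0.14 = −0.21 (better).
- Tray arms pooled by patients: PD (3 × −0.05 + 9 × −0.28)/12 = −0.2225, minus −0.21 = −0.01. RAL (3 × 0.32 + 9 × −0.35)/12 = −0.1825, minus −0.14 = −0.04.
- Equal weight to each tray arm: PD +0.045, RAL +0.125, both favouring SRP.

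**6. Source cells to check.** At week 13 HP13 PD + R-Rec = 3.43 + 3.27 = 6.70, but RAL is printed as 6.15. With 6.70 the week 4–13 gain falls from 1.14 to 0.59 mm. The SRP visit schedule lists no measurement at week 4, yet SRP week-4 values are printed.

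**The case against.** The strongest reply is that most of the reporting survives. Of the six within-arm verdicts (three arms, two measures), one is contradicted and one is implausible. HP13 PD does move in the claimed direction, and the plan does not say that the arms share an error term, so very different variances are not formally excluded. That stands. It is why the PD claim should be re-analysed and not declared false.

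The HP13 baseline R-Rec of 2.87 also looks low beside 3.23 and 3.27 later, and it feeds baseline RAL. If it were really 3.23, baseline RAL would be 7.34 and the week-4 gain 0.05 mm. The printed worsening would go, but significant improvement would still lack support.

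Some stronger readings are tempting but not supported:

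- **The trays did nothing at week 4.** The near-zero pooled difference comes from opposite arm results weighted 9 to 3. It is not evidence of no effect.
- **The Results contradict themselves on PD over time.** A repeated-measures ANOVA statement is ordinarily an omnibus test, which can coexist with a non-significant week 0–4 contrast in SRP.
- **The Discussion contradicts the Conclusion on PD.** The sentences that follow cite test-versus-control differences, so the Discussion most naturally makes a between-arm statement. It then agrees with the figures, but the Abstract and Conclusion omit it.
- **The no-recession statement is refuted.** HP13 R-Rec rose by 0.36 mm, but pooled by patients the change is (3 × 0.36 − 9 × 0.06)/12 = +0.045 mm against +0.07 in SRP.
- **The SEs, and so the tests, are site-level.** Read as patient-level, the PD SEs imply a between-patient SD of 0.06 × √3 = 0.10 to 0.04 × √9 = 0.12 mm, which seems small. But a model-based SE would also fit, and baseline RAL shows no such tension (p = 0.20). The unit is unstated and can only be inferred.

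Finally, the second primary objective speaks of inflammation, which BOP measures more directly. True, but PD and RAL are named as primary outcomes and carry the Conclusion. HP13 mean BOP did not fall by week 4 either (57% to 60%).

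**Conclusion.** The point holds in a limited form. The week-4 attachment claim is wrong for HP13 as printed: a 0.32 mm loss is reported as a significant gain. This rests only on the printed means and the definition of RAL. The HP13 PD claim (0.05 mm) is not credible beside the SRP verdict (0.21 mm), given equal n and equal printed SE and assuming one method with broadly similar visit correlation in both arms. HP26's within-arm improvement and SRP's non-significant results are compatible with the figures.

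The contrast between tray and SRP is unsupported because no between-arm PD or RAL result is given. The raw differences from SRP run in opposite directions in the two tray arms, and the pooled difference is −0.01 mm (PD) and −0.04 mm (RAL) when patients are weighted equally. None of this shows that the gel has no effect; two arms of three patients cannot settle that.

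**What to change.** 1. Withdraw the HP13 week-4 attachment claim from the Abstract and Conclusion. Withdraw the HP13 PD claim as well unless a patient-level re-analysis supports it.
2. Replace the significant/not-significant contrast with baseline-adjusted week-4 differences and confidence intervals for each tray arm against SRP. The pooled tray arms may be added, since both follow the same regimen to week 13, but the plan does not specify pooling and it should be labelled as an addition.
3. Use the patient as the unit: one mouth mean per patient per visit, or a site-level mixed model with patient and tooth effects and small-sample degrees of freedom. Report the SD of change, degrees of freedom and p-values.
4. State the unit behind the printed standard errors for PD, R-Rec and RAL, and whether the repeated-measures statement is an omnibus result.
5. Check against source data the HP13 baseline R-Rec (2.87), the HP13 week-13 RAL (6.15 against 6.70) and the mislabelled 3.21. Establish when the SRP week-4 values were taken.

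The cost is a re-analysis of data already recorded on 15 completers and text edits. A three-arm ANCOVA with a baseline covariate leaves 15 − 4 = 11 residual degrees of freedom, so the intervals for the three-patient arms will be wide and the week-4 message weaker.
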